## Statistical Analysis Plan for CLM-INS-004

Version: Final 2.0

Date: 9th September 2022

- Quality of sleep rating (rated 1 (awful) to 10 (excellent))

Compliance of entry into the digital sleep diary will be assessed as follows:

- Entry compliance: Number and % of patients who used the diary at least once (i.e entered at least one data point into the diary)
- Completion compliance: Number and % of participants completing the digital sleep diary on at least 17 out of 21 days.
- Overall diary compliance rate derived as:
  - (number of days sleep diary completed/21)\*100%

Sleep diary data will be listed and summarized based on the stage 2 analysis set only. If any sleep variables cannot be determined at a timepoint (due to partial/missing data) then relevant variables will be considered missing at the affected timepoint(s) and excluded from the relevant data summaries.

### 3.4. User Experience Questionnaire

Reporting of user experience data collected from the UEQ at Day 21 will be presented in the form of summary tables (n, mean, SD and 95% CI) and bar charts for the 26 individual items and the 6 domain scores.

Means will be derived for each domain (attractiveness, perspicuity, efficiency, dependability, stimulation and novelty) as described via the online help tool (<https://www.ueq-online.org/>). The means and 95% CIs will then be presented graphically in bar chart form for each domain and also for individual items.

UEQ values between -0.8 and 0.8 represent a more or less neutral evaluation of the corresponding scale, values > 0.8 represent a positive evaluation and values < -0.8 represent a negative evaluation.

Note: Individual response values for individual questions will either be subtracted from 4 or have 4 subtracted from them as per the online guidance depending on the whether the items starts as a positive/ negative scale. For example, items starting with a positive scale will be derived as (4-recorded score) and items starting with a negative scale will be derived as (recorded score-4).

Each participant will then have a score derived for each of the domains based on a subset of responses per domain. These will then be used to derive the domain means and CIs. CIs will be derived as follows using the mean, SD and n per domain:

$$\bar{x} \pm 1.96 \left( \frac{\sigma}{\sqrt{n}} \right)$$

### 3.5. Adverse Events

The number of reported AEs in this study is expected to be low. Therefore, AE data will not be coded by MedDRA. Data will be listed as per the CRF entries.

Statistical Analysis Plan for CLM-INS-004

Version: Final 2.0

Date: 9th September 2022

The number and % of patient will be summarized for the following AE categories:

- Any AE
- Any SAE
- Any diary related AE (where “Possibly”, “Likely”, or “Definitely” is recorded for the AE relationship question on the eCRF)

AEs will be summarized based on the stage 2 analysis set only.

### **3.6. Association of breast cancer characteristics and sleep**

To assess any association with treatment/clinical characteristics and insomnia severity, sleep efficiency and Quality of Life, data will be reported and summarized by the following characteristics for the stage 2 analysis set:

- Breast cancer stage
  - Stage I, II or III
- Treatment regime
  - Systemic, dexamethasone, radiotherapy, hormonal or targeted
- Prior chemotherapy
  - No prior chemotherapy
  - Prior chemotherapy started  $\leq$  3 months of study entry
  - Prior chemotherapy started  $>3$  and  $\leq$  6 months of study entry
  - Prior chemotherapy started  $>$  6 months of study entry
- Baseline insomnia severity
  - subthreshold, moderate, and severe
  - Note no patient should have category of “none” for the baseline assessment since they have to have insomnia to be eligible for Stage 2

The following summary tables will be presented for the above baseline/disease characteristics:

- Insomnia severity at baseline and day 21 (for breast cancer stage, treatment and prior chemotherapy only)
- Sleep efficiency % (average of last 2 weeks)
- EQ-5D-5L, summary of 5 dimensions and VAS at baseline and day 21
- FACT-ES subscale scores, FACT-G and total-ES score at baseline and day 21

In addition to tabular summarises the following plots will be produced

- Bar charts of insomnia severity (for stage, treatment and prior chemotherapy only)
- Line plots of mean daily sleep efficiency (%) over time

Statistical Analysis Plan for CLM-INS-004

Version: Final 2.0

Date: 9th September 2022

- Boxplots of FACT-ES subscale scores, FACT-G and total-ES score at baseline and day 21

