7.4.4 Clinical Data Capture

Upon receiving and reviewing completed Stage 2-specific ICF, the study team will review patient medical records and capture required data for the following eCRFs:

Cancer Medical History: capturing data regarding, time since cancer diagnosis, cancer stage, primary or secondary cancer, surgery type, neoadjuvant or adjuvant treatment, and positivity for oestrogen receptors (ER), progesterone receptors (PR) or human epidermal growth factor receptor 2 (HER2).

Cancer Treatment: current breast cancer treatment broken down by chemotherapy, radiotherapy, and hormonal therapy and information regarding current medication cycle.

Current Co-morbidities: current co-morbidities and whether each co-morbidity is being treated with medication.

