### **3.1.5. Breast Cancer treatments**

Previous and current Breast cancer treatment will be summarized for the stage 2 analysis set only based on the following:

- Current systemic anti-cancer therapy
- Time since start of current systemic anti-cancer therapy
- Number of cycles of current systemic anti-cancer therapy
- Dexamethasone treatment (Y/N)
- Time since start of dexamethasone treatment (for applicable patients)
- Radiation therapy? (Y/N)
- Time since start of radiation therapy
- Hormonal treatment? (Y/N)
- Current hormonal treatment (for applicable patients)
- Time since start of hormonal treatment (for applicable patients)
- Targeted therapy for HER2 positive breast cancer? (Y/N)
- Current targeted therapy (for applicable patients)
- Time since start of targeted therapy (for applicable patients)

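### SAP 3.6 groups outcomes by five overlapping treatments with no group not receiving each one, so differences between the groups cannot be read as associations with a given treatment

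*SAP*

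**What the plan says.** SAP 3.6 summarises insomnia severity, sleep efficiency, EQ-5D-5L and FACT-ES in the Stage 2 analysis set by four characteristics: cancer stage, treatment regime, prior chemotherapy and baseline insomnia severity. The levels of treatment regime are "Systemic, dexamethasone, radiotherapy, hormonal or targeted". The section gives no rule for a patient on more than one of these and no level for a patient on none.

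SAP 3.1.5 holds the underlying data as separate items: "Dexamethasone treatment (Y/N"), "Radiation therapy? (Y/N"), "Hormonal treatment? (Y/N") and "Targeted therapy for HER2 positive breast cancer? (Y/N"), alongside an item for current systemic anti-cancer therapy.

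Prior chemotherapy, which SAP section 4 lists as an addition to the protocol, does have a level for patients with none. Its other levels are all of the form "Prior chemotherapy started" followed by an interval before study entry (up to 3 months, over 3 and up to 6, over 6). For timing of systemic treatment, SAP 3.1.5 lists "Time since start of current systemic anti-cancer therapy". Protocol 7.4.4 lists "current breast cancer treatment broken down by chemotherapy, radiotherapy, and hormonal therapy and information regarding current medication cycle". Protocol 7.4.4 also captures whether treatment was neoadjuvant or adjuvant, SAP 3.1.4 has a neoadjuvant yes/no item, and the lead-in to SAP 3.1.5 refers to previous as well as current treatment.

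**The concern.** Even a descriptive look at association needs patients with the characteristic set against patients without it. Cancer stage, prior chemotherapy and baseline severity each divide patients into separate groups. Treatment regime does not. Someone on systemic therapy with dexamethasone and a targeted drug counts under three levels, while someone on no current treatment disappears from the factor. A reader comparing the hormonal and systemic results, for example, would be comparing groups with an unknown number of patients in common.

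The chemotherapy bands raise a related but smaller problem. A patient who began 5 months ago and is still on treatment shares the middle band with one who began 5 months ago and has finished.

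The stake is a secondary objective. Protocol section 2 says the results will inform the eligibility criteria and choice of assessments for a future trial, so a contrast blurred by the grouping could carry over into that design. The primary prevalence estimate is not affected.

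**Working it through.** **The plan's own numbers.** No figure in the documents sizes the treatment subgroups. The relevant total is the Stage 2 target: 285 × 0.44 = 125.4, and 125 × 0.80 = 100 completers, which reproduces Protocol 10.1 and SAP 1.2.1. The illustrations below use n = 100 where they need a total. All other inputs are assumed, because the documents give no treatment frequencies.

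**Can the groups overlap?** Five separately recorded items allow 2^5 = 32 treatment patterns, one of which is none. Only five patterns (exactly one treatment each) fit a set of exclusive groups. If each item applied independently with probability q, then none = (1 − q)^5, exactly one = 5q(1 − q)^4, and two or more is the remainder:

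| q (assumed) | in no group | in two or more | five group sizes sum to (per 100 patients) |
|---|---|---|---|
| 0.2 | 33% | 26% | 100 |
| 0.4 | 8% | 66% | 200 |
| 0.6 | 1% | 91% | 300 |

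Independence is a simplification. The first row shows that group sizes summing to 100 would not reveal the overlap.

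**What sharing does to a difference.** Take two equal-sized groups A and B with a fraction s of each shared. Assume the outcome is 60% in A only, 40% in B only and 50% in patients on both.

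- A shows 0.50s + 0.60(1 − s), and B shows 0.50s + 0.40(1 − s).
- The difference shown is 0.20(1 − s), because the shared patients cancel.
- s = 0.25 gives 15 points, s = 0.50 gives 10, and s = 0.75 gives 5, against 20 with no sharing.

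If one group lies wholly inside another and makes up a fraction f of it, and its patients differ by 20 points from the rest of the larger group, the two differ by 20(1 − f): 16, 10 or 4 points at f = 0.2, 0.5 or 0.8. If the groups differ in size and overlap only partly, the outcome of the shared patients also enters, so the distortion has no fixed size.

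**What a yes/no split would offer.** It yields two groups with no patient in common. For 60% versus 40% among 100 patients (two-sided 5% level, pooled variance under the null), power is about 23%, 36% or 52% when 10%, 20% or 50% of patients are treated. The exact 95% interval around an observed 50% is 35.5% to 64.5% at n = 50 and 27.2% to 72.8% at n = 20. The split is therefore interpretable but imprecise, and suited to description only.

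**Chemotherapy bands.** Set side by side, SAP 3.6 needs a start date for every course of prior chemotherapy, while the only listed timing item for systemic treatment concerns the current course. The neoadjuvant and adjuvant items show that earlier treatment is captured in part, but no listed item gives the agent, the dates or the completion status of a finished course.

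**The case against.** The strongest reply is that the plan is descriptive. Protocol 10.3.3 and SAP 3.6 promise summaries by characteristic with no test or model. A summary of everyone on hormonal therapy is valid whoever else they overlap with, and SAP 2.1 says all data will also be listed. This stands against anyone who infers that the objective cannot be answered: the documents do not support that. It does not remove the point, since SAP 3.6 states its purpose as assessing association, and listings do not give a reader of the tables an exposed and an unexposed group.

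Second, SAP 3.6 names a factor, not a layout. Table templates sit in a separate document that is not available here, and most of the items in SAP 3.1.5 are already yes/no, so a yes/no layout may be intended. That is possible. The SAP is what the templates are to be based on, however, and it does not say so.

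Third, the gap on finished chemotherapy is narrow. The case report form is not among the documents and may hold the dates. A reader might infer that patients with a finished course and no date would fall into the no-prior-chemotherapy group. No rule says this, and SAP 2.5 treats missing data as missing. Nor does the lack of an untreated group extend to this factor, which has one.

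Fourth, a yes/no split is itself confounded. If dexamethasone users are mostly on systemic therapy, those not on dexamethasone include patients on no systemic therapy at all. This stands: the split should not be presented as recovering the effect of a treatment.

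**Conclusion.** The point holds for the treatment-regime factor. Its five groups are not mutually exclusive and it has no group not receiving each treatment, so differences between the groups cannot be read as associations with a given treatment. That the groups can overlap follows from the separate items in SAP 3.1.5. How many patients are shared is unknown. The loss of half of a 20-point difference at 50% sharing is an illustration on assumed inputs, not an estimate for this study.

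The chemotherapy point is secondary. Bands by start date mix ongoing and finished courses, and the listed items do not supply what is needed to place a finished course. Whether the case report form does so cannot be judged from these documents.

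The summary of each treated group remains valid. The change is worth making because it improves a secondary objective with data already listed. The results would stay descriptive, unadjusted for co-treatment, and sparse in places.

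**What to change.** In SAP 3.6:

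- Replace the five regime levels with a yes versus no tabulation for each treatment, built from the items in SAP 3.1.5. For systemic therapy, count as no those with no current systemic therapy recorded.
- Add a row for patients on none of the five.
- State that a patient may count under several treatments, and that the contrasts are descriptive and unadjusted for co-treatment.

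This costs SAP wording and table shells only and needs no new data. Some cells will be small.

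For prior chemotherapy:

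- Name the source field for the start date.
- Separate ongoing from completed courses where the records allow.
- Show patients with prior chemotherapy but no start date as missing, not as having had no prior chemotherapy.

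If the case report form does not already hold start and end dates, this means adding two dates to the medical-record review under Protocol 7.4.4.

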## 4. CHANGES FROM THE PROTOCOL

- Clarification of analysis sets to be used to summarize Stage 1 and Stage 2 data.
- For EQ-5D-5L, individual health index values will not be derived since these are generally more relevant for treatment intervention studies that require quality-adjusted life years (QALYs) to be derived for use in informing economic evaluations of health care interventions. Instead, the data will be summarised descriptively based on the 5 level health states reported for each domain.
- Due to the expected low number of AEs, events will not be coded by MedDRA but will be reported as recorded on the CRF.
- Prior chemotherapy has been added for the secondary endpoint assessing associations between severity of insomnia and clinical or treatment characteristics of breast cancer patients.

## Statistical Analysis Plan for CLM-INS-004

Version: Final 2.0

Date: 9th September 2022**5. APPENDICES****APPENDIX A****FACT-ES Scoring Guidelines (Version 4) – Page 1**

Instructions:\*

1. Record answers in "item response" column. If missing, mark with an X
2. Perform reversals as indicated, and sum individual items to obtain a score.
3. Multiply the sum of the item scores by the number of items in the subscale, then divide by the number of items answered. This produces the subscale score.
4. Add subscale scores to derive total scores (TOI, FACT-G, FACT-ES-19 and FACT-ES-23).
5. **The higher the score, the better the QOL.**

Subscale	Item Code	Reverse item?	Item response	Item Score
PHYSICAL WELL-BEING (PWB)	GP1	4	-	= _____
	GP2	4	-	= _____
	GP3	4	-	= _____
	GP4	4	-	= _____
	GP5	4	-	= _____
	GP6	4	-	= _____
	GP7	4	-	= _____

*Score range: 0-28**Sum individual item scores: \_\_\_\_\_**Multiply by 7: \_\_\_\_\_**Divide by number of items answered: \_\_\_\_\_ =PWB***subscale score**

SOCIAL/FAMILY WELL-BEING (SWB)	GS1	0	+	_____	= _____
	GS2	0	+	_____	= _____
	GS3	0	+	_____	= _____
	GS4	0	+	_____	= _____
Score range: 0-28	GS5	0	+	_____	= _____
	GS6	0	+	_____	= _____
	GS7	0	+	_____	= _____

*Sum individual item scores: \_\_\_\_\_**Multiply by 7: \_\_\_\_\_**Divide by number of items answered: \_\_\_\_\_ =SWB***subscale score**

EMOTIONAL WELL-BEING (EWB)	GE1	4	-	_____	= _____
	GE2	0	+	_____	= _____
	GE3	4	-	_____	= _____
	GE4	4	-	_____	= _____
Score range: 0-24	GE5	4	-	_____	= _____
	GE6	4	-	_____	= _____

*Sum individual item scores: \_\_\_\_\_**Multiply by 6: \_\_\_\_\_**Divide by number of items answered: \_\_\_\_\_ =EWB*

## Statistical Analysis Plan for CLM-INS-004

Version: Final 2.0

Date: 9th September 2022**subscale score****FUNCTIONAL**

GF1 0 + \_\_\_\_\_ = \_\_\_\_\_

**WELL-BEING**

GF2 0 + \_\_\_\_\_ = \_\_\_\_\_

**(FWB)**

GF3 0 + \_\_\_\_\_ = \_\_\_\_\_

GF4 0 + \_\_\_\_\_ = \_\_\_\_\_

*Score range: 0-28*

GF5 0 + \_\_\_\_\_ = \_\_\_\_\_

GF6 0 + \_\_\_\_\_ = \_\_\_\_\_

GF7 0 + \_\_\_\_\_ = \_\_\_\_\_

*Sum individual item scores: \_\_\_\_\_**Multiply by 7: \_\_\_\_\_**Divide by number of items answered: \_\_\_\_\_ =FWB***subscale score****19 ITEM**

ES1 4 - \_\_\_\_\_ = \_\_\_\_\_

**ENDOCRINE**

ES2 4 - \_\_\_\_\_ = \_\_\_\_\_

**SYMPTOM**

ES3 4 - \_\_\_\_\_ = \_\_\_\_\_

**SUBSCALE**

ES4 4 - \_\_\_\_\_ = \_\_\_\_\_

**(ESS-19)**

ES5 4 - \_\_\_\_\_ = \_\_\_\_\_

*Score range: 0-76*

ES6 4 - \_\_\_\_\_ = \_\_\_\_\_

ES7 4 - \_\_\_\_\_ = \_\_\_\_\_

ES8 4 - \_\_\_\_\_ = \_\_\_\_\_

ES9 4 - \_\_\_\_\_ = \_\_\_\_\_

ES10 4 - \_\_\_\_\_ = \_\_\_\_\_

An9 4 - \_\_\_\_\_ = \_\_\_\_\_

O2 4 - \_\_\_\_\_ = \_\_\_\_\_

C5 4 - \_\_\_\_\_ = \_\_\_\_\_

An10 4 - \_\_\_\_\_ = \_\_\_\_\_

Tax1 4 - \_\_\_\_\_ = \_\_\_\_\_

ES11 4 - \_\_\_\_\_ = \_\_\_\_\_

ES12 4 - \_\_\_\_\_ = \_\_\_\_\_

ES13 4 - \_\_\_\_\_ = \_\_\_\_\_

BRM1 4 - \_\_\_\_\_ = \_\_\_\_\_

*Sum individual item scores: \_\_\_\_\_**Multiply by 19: \_\_\_\_\_**Divide by number of items answered: \_\_\_\_\_ =ES***Subscale score****To Derive a FACT-G total score:***Score range: 0-108*

\_\_\_\_\_ + \_\_\_\_\_ + \_\_\_\_\_ + \_\_\_\_\_ = \_\_\_\_\_ =FACT-G

Statistical Analysis Plan for CLM-INS-004

Version: Final 2.0

Date: 9th September 2022

**Total score**  
(PWB score) (SWB score) (EWB score) (FWB score)

**To Derive a FACT-ES total score:**

*Score range:* 0-184

$\frac{(\text{PWB score})}{(\text{PWB score})} + \frac{(\text{SWB score})}{(\text{SWB score})} + \frac{(\text{EWB score})}{(\text{EWB score})} + \frac{(\text{FWB score})}{(\text{FWB score})} + \frac{(\text{ESS-19 score})}{(\text{ESS-19 score})} = \underline{\hspace{2cm}} = \text{FACT-ES Total score}$

